Part 1b is a 2-period, cross-over study and will evaluate the effect of food on the safety, tolerability, and pharmacokinetics of a single dose of 1500 mg gepotidacacin tablet formulation selected from Part 1a. If both formulations of the free base tablet exhibit similar bioavailability to the capsule formulation, then the results of the moderate fat meal evaluated in the RC mesylate tablet formulation from Study BTZ117349 (GlaxoSmithKline Document Number [2013N176846_01](#) Study ID BTZ117349) will be used to guide dosing recommendations with food. See the study schematic in [Table 2](#) for more details.

Subjects will participate in 2 treatment periods and blood samples will be collected for PK analysis of gepotidacacin concentrations according to the Time and Events Table ([Table 9](#)). Blood samples will be collected up to approximately 48 hours after dosing.

Table 2 Part 1b Food Effect Study Design Schematic

Treatment	Cross-over			Follow-up
	Period 1	Wash-out At least 3 days	Period 2	
RC or HSWG tablet fasted ^a				5 to 7 days after final dose
RC or HSWG tablet fed ^a				
Sequence 4	D		E	
Sequence 5	E		D	

HSWG = high shear wet granulation; RC = related compound.

^a 1500 mg single dose given as 2 × 750 mg tablets fasted (Treatment D) and fed (Treatment E)

Part 2: Pharmacokinetics in Japanese Subjects

Part 2 is a 2-period, fixed-sequence study and will evaluate the pharmacokinetics of a single dose of 1500 mg followed by a single dose of 3000 mg gepotidacacin tablet formulation selected from Part 1a in a cohort of Japanese subjects under fasted conditions. See the study schematic in [Table 3](#) for more details.

Subjects will participate in 2 treatment periods and blood and urine samples will be collected for PK analysis of gepotidacin concentrations according to the Time and Events Table ([Table 9](#)). Blood and urine samples will be collected up to approximately 48 hours after dosing.

Table 3 Part 2 Pharmacokinetic Study Design Schematic

Treatment	Fixed-sequence				Follow-up
RC or HSWG tablet ^a	Period 1	Wash-out At least 3 days	Period 2	Wash-out At least 3 days	5 to 7 days after final dose
Sequence 6	B or C		F		

HSWG = high shear wet granulation; RC = related compound.

^a 1500 mg single dose given as 2 × 750-mg RC (Treatment B) or HSWG (Treatment C) tablets; 3000 mg single dose given as 4 × 750-mg RC or HSWG tablets (Treatment F)

Part 3: Pharmacokinetics in Japanese Subjects - Fed State

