Part 3 is a 3-period, randomized, double-blind, placebo-controlled, fixed-sequence study and will evaluate the safety, tolerability, and pharmacokinetics of single ascending doses of 1500 mg, 2250 mg, and 3000 mg gepotidacin tablet formulation selected from Part 1a or placebo in a cohort of Japanese subjects in the fed state. See the study schematic in [Table 4](#) for more details.

Table 4 Part 3 Pharmacokinetic Study Design Schematic - Fed State

Treatment	Fixed-sequence					Follow-up
RC, HSWG, or placebo tablet - fed ^a	Period 1	Wash-out At least 3 days	Period 2	Wash-out At least 3 days	Period 3	5 to 7 days after final dose
Sequence 7	E or I		G or I		H or I	

HSWG = high shear wet granulation; RC = related compound.

^a 1500 mg single dose given as 2 × 750-mg RC or HSWG (Treatment E) tablets – fed; 2250 mg single dose given as 3 × 750-mg RC or HSWG (Treatment G) tablets – fed; 3000 mg single dose given as 4 × 750-mg RC or HSWG (Treatment H) tablets – fed; or placebo (Treatment I) tablets – fed

Subjects will be stratified by gender in a 1:1 ratio and randomly assigned (10 active: 2 placebo) to receive gepotidacin or placebo. For each period, a sentinel group of up to 4 subjects will be dosed with study drug and evaluated for safety and tolerability prior to dosing the remaining subjects. The adverse event profiles will be reviewed before escalating to the next dose. Subjects will participate in 3 treatment periods and blood and urine samples will be collected for PK analysis of gepotidacin concentrations according to the Time and Events Table ([Table 9](#)). Blood and urine samples will be collected up to approximately 48 hours after dosing.

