On Day 1 (Period 1), subjects will receive a single 1500-mg (2×750 mg) dose of gepotidacin tablet (RC or HSWG) selected from Part 1a. On Day 1 of Period 2, subjects will receive a single 3000-mg (4×750 mg) dose of gepotidacin tablet (RC or HSWG) selected from Part 1a. There will be a washout period of at least 3 days between doses.

Subjects will remain in the clinical research unit from Day -1 until Day 3 of Period 2 after all scheduled PK and safety assessments have been completed, and will return to the clinic for a Follow-up visit approximately 5 to 7 days after the final dose of study drug. The duration of the study (from Screening to the Follow-up visit) will be approximately 41 days.

Part 3: Pharmacokinetics in Japanese Subjects - Fed State

- Treatment E: Gepotidacin 1500 mg (2 × 750 mg) RC or HSWG tablets - fed
- Treatment G: Gepotidacin 2250 mg (3 × 750 mg) RC or HSWG tablets - fed
- Treatment H: Gepotidacin 3000 mg (4 × 750 mg) RC or HSWG tablets - fed
- Treatment I: Placebo tablets - fed

On Day 1 (Period 1), subjects will be stratified by gender in a 1:1 ratio and randomly assigned (10 active: 2 placebo) to receive gepotidacin tablet (RC or HSWG) selected from Part 1a in an ascending manner (Treatments E, G, and H) on Day 1 of Periods 1, 2, and 3, respectively, or placebo. For each period, a sentinel group of up to 4 subjects will be dosed with study drug and evaluated for safety and tolerability prior to dosing the remaining subjects. There will be a washout period of at least 3 days between doses. The adverse event profiles will be reviewed before escalating to the next dose. Subjects will remain in the clinical research unit from Day -1 until Day 3 of Period 3 after all scheduled PK and safety assessments have been completed, and will return to the clinic for a Follow-up visit approximately 5 to 7 days after the final dose of study drug. The duration of the study (from Screening to the Follow-up visit) will be approximately 44 days.

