7.3.1. Adverse Events and Serious Adverse Events

The definitions of an AE or SAE can be found in [Appendix 5](#).

The investigator and their designees are responsible for detecting, documenting, and reporting events that meet the definition of an AE or SAE.

7.3.1.1. Time Period and Frequency for Collecting Adverse Event and Serious Adverse Event information

- Any SAEs assessed as related to study participation (e.g., protocol-mandated procedures, invasive tests, or change in existing therapy) or related to a GSK product will be recorded from the time a subject consents to participate in the study up to and including any follow-up contact.
- AEs will be collected from the time informed consent is obtained until the follow-up contact (see Section 7.3.1.3), at the time points specified in the Time and Events Table (Table 9).
- Medical occurrences that begin prior to the start of study treatment but after obtaining informed consent may be recorded on the Medical History/Current Medical Conditions section of the eCRF.
- All SAEs will be recorded and reported to GSK within 24 hours, as indicated in [Appendix 5](#).
- Investigators are not obligated to actively seek AEs or SAEs in former study subjects. However, if the investigator learns of any SAE, including a death, at any time after a subject has been discharged from the study, and he/she considers the event reasonably related to the study treatment or study participation, the investigator must promptly notify GSK.

NOTE: The method of recording, evaluating and assessing causality of AEs and SAEs plus procedures for completing and transmitting SAE reports to GSK are provided in [Appendix 5](#).

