9.4.2. Secondary Analyses

Safety Analyses

The following safety evaluations will be performed:

- Monitoring for AEs
- Changes in routine clinical laboratory parameters including serum chemistry, hematology, and urinalysis
- Clinically significant changes in vital sign measurements or physical examination findings
- Changes in 12-lead ECG measurements

Safety endpoints will include AEs, clinical laboratory results (serum chemistry [including liver function parameters], hematology, and urinalysis), vital sign measurements (systolic and diastolic blood pressure and heart rate), 12-lead ECG measurements, and physical examination findings.

All safety data will be presented in the data listings. Subject demographics, medical history, and prior and concomitant medications will be summarized by group using descriptive statistics. For continuous variables, these summaries will include sample size, mean, median, SD, minimum, and maximum.

For categorical variables, the summaries will include frequencies and corresponding percentages. No inferential hypothesis testing will be performed on the safety variables.

Adverse events will be coded using the MedDRA classification system.

Treatment-emergent AEs will be defined as any AEs, regardless of relationship to investigational product, that occur after the dose of investigational product. All AEs will be summarized by group at AE onset for the overall number of AEs and the percentage of subjects who experience them. The total number of AEs will be summarized by group and overall. Listings for the subsets of SAEs and treatment-related SAEs will be provided. The number of SAEs will be summarized. The incidence of AEs will also be summarized by system organ class and preferred term.

Clinical laboratory results, vital sign measurements (systolic and diastolic blood pressure and heart rate), and 12-lead ECG results will be summarized by change from baseline. Clinical laboratory values that are outside of the reference ranges will be flagged and evaluated for clinical significance by the investigator. Any ECG abnormalities, including but not limited to a QTc >500 msec or increase in QTc from the baseline ECG of ≥ 60 msec, will be summarized by group.

Detailed descriptions of the analyses in this study will be presented in the RAP.

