10.2.1.2. Treatment States for AE Data

Treatment State	Definition
Pre-Treatment	AE Start Date/Time < Study Treatment Start Date/Time
On-Treatment	If AE onset date/time is on or after treatment start date/time & on or before the treatment stop date/time with 2 days lag time Study Treatment Start Date/Time ≤ AE Start Date/Time ≤ Study Treatment Stop Date/Time + 2 Days
Post-Treatment	If AE onset date/time is after the treatment stop date/time with 2 days lag time AE Start Date/Time > Study Treatment Stop Date/Time + 2 days
Onset Time	If Treatment Start Date/Time > AE Onset Date/Time = AE Onset Date - Treatment Start Date
Since First Dose (Days)	If Treatment Start Date/Time ≤ AE Onset Date/Time = AE Onset Date - Treatment Start Date +1 Missing otherwise
Duration (Days)	AE Resolution Date – AE Onset Date + 1
Drug-related	If relationship is marked 'YES' on eCRF OR value is missing

NOTES:

- If the study treatment stop date is missing then the AE will be considered to be On-Treatment.

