10.11.5. Safety Tables

Safety Tables					
No.	Population	IDSL / TST ID / Example Shell	Title	Programming Notes	Deliverable [Priority]
Adverse Events					
2.1	Safety	AE1	Summary of All Adverse Events		IA [1], SAC [1]
2.2	Safety	AE1	Summary of All Drug- Related Adverse Events		IA [1], SAC [1]
2.3	Safety	AE15	Summary of Common (>=25%) Non-serious Adverse Events by System Organ Class and Preferred Term (Number of Subjects and Occurrences)		IA [1], SAC [1]
2.4	Safety	AE16	Summary of Serious Adverse Events by System Organ Class and Preferred Term (Number of Subjects and Occurrences)		IA [1], SAC [1]
Laboratory Measurements					
2.5	Safety	LB1	Summary of Clinical Chemistry Change from Baseline		SAC [1]
2.6	Safety	LB1	Summary of Haematology Change from Baseline		SAC [1]
2.7	Safety	UR3b	Summary of Urinalysis Dipstick Results		SAC [1]
Electrocardiograms					
2.8	Safety	EG1	Summary of ECG Findings		SAC [1]
2.9	Safety	SAFE_T1	Summary of Frequency of Maximum Post-Dose ECG Parameter Corrected QTc Interval		SAC [1]
2.10	Safety	SAFE_T2	Summary of Frequency of Maximum Change from Baseline for ECG Parameter Corrected QTc Interval		SAC [1]
2.11	Safety	EG2	Summary of Change from Baseline in ECG Values		SAC [1]
Vital Signs					
2.12	Safety	VS1	Summary of Change from Baseline in Vital Signs		SAC [1]

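### In fixed-sequence Parts 2 and 3, the by-dose AE tables observe 3000 mg until Follow-up but each lower dose only until the next dose, so later-onset AEs can raise the 3000-mg percentage without a dose effect

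*Protocol*

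**What the plan says.** **AE rule.** Protocol 7.3.1.1 sets the collection period: "AEs will be collected from the time informed consent is obtained until the follow-up contact". Protocol 9.4.2 treats any AE after the dose as treatment-emergent, with no upper time limit, and then states: "All AEs will be summarized by group at AE onset for the overall number of AEs and the percentage of subjects who experience them".

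**Timing.** Protocol 4.2 says of each multi-period part: "There will be a washout period of at least 3 days between doses". Subjects then return for "a Follow-up visit approximately 5 to 7 days after the final dose of study drug". The stated durations from Screening to Follow-up are approximately 41 days for Part 2 and 44 days for Part 3.

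**Design.** Protocol 4.1: "Part 2 is a 2-period, fixed-sequence study" (1500 mg, then 3000 mg) and "Part 3 is a 3-period, randomized, double-blind, placebo-controlled, fixed-sequence study" (1500, 2250, then 3000 mg, or placebo throughout). For subjects on active drug, 3000 mg is always the last dose.

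**SAP.** Section 10.11.5 lists the AE tables, starting with Table 2.1, "Summary of All Adverse Events". Tables 2.1 to 2.4 carry no window restriction and no programming note. Section 10.2.1.2 defines On-Treatment AEs, per treatment period, as "Study Treatment Start Date/Time ≤ AE Start Date/Time ≤ Study Treatment Stop Date/Time + 2 Days", and calls later AEs Post-Treatment. No display is linked to either state. SAP 2.1 declares one change from the protocol analysis, the Part 3 power model, so the protocol's AE rule stands.

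**The concern.** Assigning an AE to the dose in force at onset gives each dose an observation window. That window ends at the next dose for a lower dose, and at Follow-up for the last dose. In Part 1a the Latin square puts each formulation last in one sequence of three, so the longer final window is shared evenly. Parts 2 and 3 have no such balance: the longer window always belongs to 3000 mg. A percentage of subjects with an AE rises with the time observed, so the columns are not like for like.

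Safety and tolerability by dose is a secondary objective of both parts. Appendix 11 of the protocol says that Part 3 was added because of tolerability at 3000 mg in Part 2. With about 10 subjects on active drug in each part, one extra affected subject moves a percentage by 10 points. SAP 10.3.1 provides a single placebo group, so no period-matched placebo column would reveal the pattern.

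**Working it through.** **1. Planned gap between doses.** Inputs from Protocol 4.2: 30 days of screening before Day -1, one day from Day -1 to dosing, a gap of g days between doses, and Follow-up up to 7 days after the last dose.

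Duration = 30 + 1 + g × (periods − 1) + 7. With g = 3:

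- two periods: 30 + 1 + 3 + 7 = 41 (stated: 41)
- three periods: 30 + 1 + 6 + 7 = 44 (stated: 44)

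With g = 4 the totals would be 42 and 46. The difference 44 − 41 = 3 does not depend on the screening or Follow-up lengths. The totals fit a 3-day gap, but the protocol gives them as approximate and 3 days as a minimum.

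**2. Ratio of observation times, 3000 mg to a lower dose.**

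| Gap between doses | Follow-up at day 5 | Follow-up at day 7 |
|---|---|---|
| 3 days | 5/3 = 1.67 | 7/3 = 2.33 |
| 5 days | 5/5 = 1.0 | 7/5 = 1.4 |
| 7 days | 5/7 = 0.71 | 7/7 = 1.0 |

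**3. Upper illustration: constant AE rate, no dose effect (assumption).** The documents give no AE rate over time. If the 3-day risk is p, the risk over T days is 1 − (1 − p)^(T/3).

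| 3-day risk, lower doses | 3000 mg, 5 days | 3000 mg, 7 days |
|---|---|---|
| 5% | 8.2% | 11.3% |
| 10% | 16.1% | 21.8% |
| 20% | 31.1% | 40.6% |

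At p = 20%, with 10 subjects per dose treated as independent binomials (a simplification, since the same subjects take each dose), the chance that 3000 mg shows more affected subjects than 1500 mg is 0.39 with equal 3-day windows. It is 0.62 with 5 days and 0.78 with 7 days.

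**4. Mainly acute AEs (assumption).** Let a be the risk of an AE within 48 hours of dosing and b the 3-day background risk. The risk over T days is 1 − (1 − a)(1 − b)^(T/3). With a = 30% and b = 5%:

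- 3 days: 1 − 0.70 × 0.95 = 33.5%
- 5 days: 35.7%
- 7 days: 37.9%

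The gap is 2.2 to 4.4 percentage points, or 0.2 to 0.4 of a subject in 10. With b = 0 it is zero.

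**5. With the SAP's dose-plus-2-days window.** Two days is shorter than the minimum gap, so the window closes before the next dose at every dose level. At p = 20% the expected risk is 1 − 0.80^(2/3) = 13.8% at each dose, and the imbalance disappears.

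**The case against.** The strongest reply is that the SAP already holds an equal window. The On-Treatment state is defined per period and is the same for every dose. SAP Section 5 lists that appendix among its general data-handling conventions, and the protocol defers detail to the SAP. On this view the gap is a missing cross-reference. That is fair as a diagnosis. But the tables as listed cover all AEs, and the SAP does not declare a change to the protocol's rule, so a programmer following the text would produce unequal windows.

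The second reply is about onset. Protocol 4.6.1 links cholinergic and GI effects to peak concentration, and Protocol 4.5 reports median Tmax of 1.25 to 3 hours and half-life of about 11 to 12 hours. This favours early onset and makes the constant-rate figures an unfavourable case. It stands, and it limits the size.

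Third, 3 days is a minimum. Part 3 also requires sentinel dosing and AE review before escalation, and its 44 days equals the total for Part 1a, which has neither step. The actual Part 3 gap may be longer. This stands too; Part 2 has no comparable step.

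Fourth, the extra days after 3000 mg are mostly outpatient, after discharge on Day 3, so AEs there may be less fully ascertained than in the unit. A ratio of days ignores this.

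Finally, safety is descriptive, drug-related AEs have their own table, and all AEs are listed. These points limit the consequence but do not make the dose columns comparable.

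**Conclusion.** The structural point holds. As written, the protocol rule and the SAP tables compare dose levels over unequal windows in Parts 2 and 3. At the 3-day gap that fits the stated durations, the imbalance runs in one direction, toward more AEs at 3000 mg.

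A reader might infer that the tables will make 3000 mg look less well tolerated whatever the truth, or that an observed excess there would be an artefact. The documents support neither. An excess from this source needs AEs that start after the lower-dose window has closed, at a rate the documents do not give. It also needs an actual gap shorter than the time from last dose to Follow-up. At a 5-day gap the ratio is 1.0 to 1.4, and at 7 days it is 0.71 to 1.0. With mostly acute AEs the distortion is about 2 to 4 percentage points under the stated assumption, or nil. Nor do the documents show a deliberate choice to compare 3 days with 5 to 7; the SAP leaves the link between treatment state and table unstated.

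This is a cheap improvement to the SAP, not a flaw that undermines the safety objective.

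**What to change.** In SAP 10.11.5, for Parts 2 and 3:

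- Build the by-dose columns of Tables 2.1 to 2.3 on AEs with onset in the existing On-Treatment state.
- Add a separate row or column, still by dose, for Post-Treatment AEs up to the next dose or Follow-up.
- Leave the SAE table (2.4) and all listings unrestricted.
- State how this sits with the protocol's open-ended treatment-emergent definition, and record it in SAP 2.1 as a change from the protocol analysis.

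The cost is SAP wording and one selection flag in programs for existing tables; no new data are needed. The downside is that late-onset events such as rash or *C. difficile* move to the separate row and must be read there. The change does not remove the confounding of dose with period, and a late effect of one dose that starts after the next dose is still counted under the later dose.

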10. STUDY GOVERNANCE CONSIDERATIONS

10.1. Posting of Information on Publicly Available Clinical Trial Registers

Study information from this protocol will be posted on publicly available clinical trial registers before enrollment of subjects begins.

10.2. Regulatory and Ethical Considerations, Including the Informed Consent Process

Prior to initiation of a site, GSK will obtain favorable opinion/approval from the appropriate regulatory agency to conduct the study in accordance with International Council for Harmonisation (ICH) Good Clinical Practice (GCP) and applicable country-specific regulatory requirements.

The study will be conducted in accordance with all applicable regulatory requirements, and with GSK policy.

The study will also be conducted in accordance with ICH GCP, all applicable subject privacy requirements, and the guiding principles of the current version of the Declaration of Helsinki. This includes, but is not limited to, the following:

- IRB/IEC review and favorable opinion/approval of the study protocol and amendments as applicable.
- Obtaining signed informed consent.
- Investigator reporting requirements (e.g., reporting of AEs/SAEs/protocol deviations to the IRB/IEC).
- GSK will provide full details of the above procedures, either verbally, in writing, or both.
- Signed informed consent must be obtained for each subject prior to participation in the study.
- The IRB/IEC, and where applicable the regulatory authority, approve the clinical protocol and all optional assessments, including genetic research.
- Optional assessments (including those in a separate protocol and/or under separate informed consent) and the clinical protocol should be concurrently submitted for approval unless regulation requires separate submission.
- Approval of the optional assessments may occur after approval is granted for the clinical protocol where required by regulatory authorities. In this situation, written approval of the clinical protocol should state that approval of optional assessments is being deferred and the study, with the exception of the optional assessments, can be initiated.

10.3. Quality Control (Study Monitoring)

- In accordance with applicable regulations including GCP and GSK/PPD procedures, GSK/PPD monitors will contact the clinic prior to the start of the study to review the following with the clinic staff: the protocol, study requirements, and their responsibilities to satisfy regulatory, ethical, and GSK/PPD requirements.
- When reviewing data collection procedures, the discussion will also include identification, agreement and documentation of data items for which the eCRF will serve as the source document.

GSK/PPD will monitor the study and clinic activity to verify that the:

- Data are authentic, accurate, and complete.
- Safety and rights of subjects are being protected.
- Study is conducted in accordance with the currently approved protocol and any other study agreements, GCP, and all applicable regulatory requirements.
- The investigator and the head of the medical institution (where applicable) agrees to allow the monitor direct access to all relevant documents.

